9.3 Variables

Exposures

The Nordic countries conduct annual influenza vaccination campaigns that focus on specific population groups at high risk of severe outcomes from influenza. These groups generally include the elderly, individuals with chronic health conditions, pregnant women, children and healthcare workers (Table 2).

The vaccines are provided free of charge and are typically administered before the peak flu season. In Denmark, vaccines for season 2024/2025 are administered from October 1st, in Finland from September 30th and in Sweden from October 15th. In immunization programmes across the three Nordic countries, the most frequently used quadrivalent inactivated influenza vaccine brands have been InfluvacTetra, VaxigripTetra, FluadTetra, FluarixTetra, and Efluelda Tetra, which are formulated

according to WHO's recommendations. The vaccines contain both seasonal influenza A subtypes, A(H3N2) and A(H1N1) pdm09, and both influenza B lineages, B/Victoria and B/Yamagata. Overview of the country-specific vaccine brands, types and target populations is provided in Table 3. At vaccination at general practitioners, regional vaccination centres or workplaces, individuals are vaccinated with the influenza vaccine available at the location.

An individual is defined as vaccinated starting from and including the day of the first influenza vaccination during the ongoing season, and as unvaccinated if they have yet to receive a first vaccine in the ongoing season.

Table 2. Influenza Vaccination Recommendations in Nordic Countries for season 2024/2025

Country	Target Groups for Influenza Vaccination

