Logistic regression models will be used to estimate the odds ratio (OR) with 95% CIs. Our main estimate of interest is the vaccine effectiveness defined by $(1-OR) \times 100\%$. The models will be adjusted for age, sex, region of residency and comorbidities. We will assess whether the frequency of testing differs between vaccinated and unvaccinated groups during the season, since differential testing could bias VE estimates. The testing frequency will be visualized in a plot stratified by month and vaccination status.

Prior event rate adjustment

A difference-in-differences approach in the form of prior event rate ratio (PERR) adjustment exists for evaluating healthy vaccinee bias for influenza outcomes. (51) The PERR method is built on the assumption that any differences in event rates unrelated to vaccination between vaccinated and unvaccinated individuals can be observed in the period before vaccination is available. This can be implemented using the pairwise version of PERR. (51)

The matching and censoring criteria from the main TTE analysis will be applied. As before, the day the seasonal vaccine dose was administered within each matched pair will serve as the index date for both individuals. For each individual within a matched pair, the pre-vaccination period will be the start of the 2024/2025 influenza season (1 October 2024) until the index date and the post-vaccination period will start on day 14 following the index date. We will identify individuals who ultimately receive a seasonal influenza vaccine (“future vaccinated”) and those who remain unvaccinated (“future unvaccinated”), evaluated at the end of the studied period or on the date of the outcome. Both groups will have the number of outcomes and the amount of person-time measured in the pre-vaccination period (to establish baseline event rates) and in the post-vaccination season (to assess post-vaccination event rates).

The outcome under study is influenza-related hospitalization. Given that influenza hospitalization may be less frequent at the start of the influenza season, we will assess whether sufficient events occur in the pre-vaccination period to produce stable estimates.

We will employ the pairwise version of PERR, which effectively compares the ratio of (current vs. pre-vaccinated) event rates in the vaccinated group to the ratio of (current vs. pre-vaccinated) event rates in the unvaccinated group. Formally:

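### The PERR grouping rule reads vaccination status at the outcome date or study end: the first empties a denominator if applied to pre-index events, the second conflicts with the matched-pair censoring

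*Protocol*

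**What the plan says.** All of this is in Protocol section 9.8, Prior event rate adjustment, unless noted.

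- **Design carried over:** "The matching and censoring criteria from the main TTE analysis will be applied". Under section 9.7 (Procedures), a recipient is matched on the vaccination day to a person not yet vaccinated. The pair is right-censored if that reference is later vaccinated, and the reference may then enter a new pair as a recipient.
- **Periods:** "the pre-vaccination period will be the start of the 2024/2025 influenza season (1 October 2024) until the index date". Follow-up for the second period opens 14 days after vaccination.
- **Groups:** "We will identify individuals who ultimately receive a seasonal influenza vaccine", as against those who stay unvaccinated, with status "evaluated at the end of the studied period or on the date of the outcome".
- **Counting:** "Both groups will have the number of outcomes and the amount of person-time measured in the pre-vaccination period", and again in the post-vaccination period.
- **Outcome:** "The outcome under study is influenza-related hospitalization".
- **Estimator:** the current-to-prior rate ratio in the vaccinated divided by the same ratio in the unvaccinated, with rates from Poisson regression and VE = 1 − PERR.
- **Status definition (section 9.3, Exposures):** a person counts as vaccinated from and including the day of the first dose, and "as unvaccinated if they have yet to receive a first vaccine in the ongoing season".

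**The concern.** PERR uses the pre-period to measure how the two groups differed before the vaccine could act. The group label must therefore not depend on whether or when the event happened. The clause makes it depend on exactly that.

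The two branches fail differently. The outcome-date branch removes pre-period events from the vaccinated group and adds them to the unvaccinated group. The end-of-period branch lets vaccination after the index date change the label of a person whom the matched design treats as a reference.

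At stake is the analysis that the Protocol introduces for evaluating healthy vaccinee bias, and that it counts among those to be triangulated with the main result. Section 9.6 has common R scripts written in Denmark and run in each country, so a literal coding would be repeated in all three.

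**Working it through.** The Protocol gives no numerical PERR result, so there is no figure to reproduce. The check is of the rule against the formula.

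**1. Outcome-date branch.**

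PERR = (Rv,cur / Rv,pre) / (Ru,cur / Ru,pre)

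- A pre-period event occurs between 1 October 2024 and the index date, which is the vaccination day.
- By section 9.3, the later vaccinee is unvaccinated on every day before that date.
- Status read on the outcome date is therefore unvaccinated, and the event goes to the unvaccinated group.
- Hence Rv,pre = 0, except for any event on the index day, which section 9.3 counts as vaccinated. PERR divides by zero and 1 − PERR is undefined. More data do not help.

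**2. Small illustration (invented counts).** Take no vaccine effect, no confounding, equal person-time, equal post-period rates r, and 20 pre-period events.

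- Correct labels, 10/10: PERR = (r/10)/(r/10) = 1, so VE = 0%.
- Outcome-date labels, 0/20: PERR = (r/0)/(r/20), undefined.
- With 0.5 added to each pre-period count: PERR = 20.5/0.5 = 41, so VE = 1 − 41 = −40, i.e. −4000%. The Protocol does not propose this correction; the line shows only that patching the zero does not rescue the estimate.

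**3. Simulation (all inputs assumed).** 500,000 pairs; index date uniform over days 1–60; 112 post-period days; true VE 0.40; post-period hazard 1e-5 per day; pre-period hazard 1e-6 or 5e-6 per day; vaccinated-to-unvaccinated baseline risk ratio 1.0 or 0.8. One run per scenario. Events are vaccinated/unvaccinated, and VE is a proportion.

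| Pre-hazard, baseline ratio | Pre-events, label fixed by pair | Post-events | VE, label fixed | Pre-events, outcome-date label | VE, outcome-date label | VE with 0.5 in the empty cell |
|---|---|---|---|---|---|---|
| 1e-6, 1.0 | 17/9 | 348/595 | 0.69 | 0/26 | −∞ | −29.4 |
| 1e-6, 0.8 | 7/18 | 271/556 | −0.25 | 0/25 | −∞ | −23.4 |
| 5e-6, 1.0 | 102/80 | 317/576 | 0.57 | 0/182 | −∞ | −199.3 |
| 5e-6, 0.8 | 60/72 | 281/580 | 0.42 | 0/132 | −∞ | −126.9 |

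Row 3 by hand: fixed label, 1 − (317/102)/(576/80) = 1 − 3.108/7.200 = 0.57. Fixing the label makes the estimate finite. It stays noisy when pre-period events are few, which is the separate problem that the Protocol does recognise.

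**4. End-of-period branch.** If status is read at study end for everyone, vaccinees keep their pre-period events and the zero disappears. Now take a reference who is vaccinated after the index date.

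- Section 9.7: a reference until that day, when the pair is censored.
- PERR clause: a member of the future-vaccinated group, so both members of that pair carry the vaccinated label.

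Both cannot hold. If the two branches are combined (outcome date for people with an event, study end for the rest), a reference hospitalised before a later vaccination stays unvaccinated while an event-free one is relabelled. That raises the unvaccinated post-period rate. The simulation has no later vaccination of references, so this effect is not quantified.

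Section 9.5 gives a rough idea of how many people could be involved: 75.6% coverage in Danes aged 65 and over by 20 December 2024. If a share c of that population is already vaccinated when a reference is chosen, and references resemble the remaining population, about (0.756 − c)/(1 − c) are vaccinated by that date. This is 75.6% at c = 0 and 0.256/0.5 = 51.2% at an assumed c = 0.5. The share falls for later index dates.

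**The case against.** The strongest reply is that the surrounding text shows a different intent. The sentence defines the vaccinated group as those who ultimately receive a dose, and a person hospitalised in early October and vaccinated later plainly does. The next sentence expects pre-period outcomes in both groups. The analysis is built on matched pairs with a shared index date, so the clause could be read as referring only to the end of post-index follow-up, in which case the labels coincide with the pair arms.

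This stands to a degree. A reader might infer that PERR is undefined on any reading. The documents do not support that, because the zero arises only when the outcome-date branch is applied to pre-index events. But nothing restricts the branch to later events, and the regression discontinuity analysis in the same section uses the same convention, so it does not look like a slip.

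A reader might also infer that the fault would go unnoticed. That goes too far: the Protocol plans to check for sufficient pre-period events, to review code and to open the scripts for comment, and a count of zero would be visible. The check would not repair the rule, however, and the only explanation that the Protocol offers for few pre-period events is early vaccination, high uptake and low early-season incidence.

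Finally, PERR is one supplementary analysis among several, on one outcome, to be interpreted with caution. That is correct and limits the importance.

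**Conclusion.** The clause is wrong as written. Its outcome-date branch, applied literally to pre-index events, gives a structural zero in the vaccinated pre-period rate and an undefined VE. It also contradicts the definition of the vaccinated group in its own sentence. Its end-of-period branch gives a finite ratio but conflicts with the pair censoring that the analysis adopts.

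The zero rests on logic alone, given the definitions in sections 9.3 and 9.8. The 0/20 split, the PERR of 41 and the simulated values are illustrations under assumed inputs and do not forecast what the study would report. No size can be put on the bias from relabelled references.

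Importance is moderate. A reader might infer that the brand-specific VE estimates are compromised; they are not, because section 9.7 sets the arms at the index date and does not use this clause. What is affected is the usability of one check on healthy vaccinee bias.

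**What to change.** In section 9.8, Prior event rate adjustment:

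- Assign the PERR group by matched-pair role at the index date: the member vaccinated that day is vaccinated, and the matched reference is unvaccinated.
- Keep that label for both the pre- and post-periods, regardless of when an outcome occurs.
- Count pre-period events and person-time from 1 October 2024 to the index date for both members.
- In the post-period, censor the pair when the reference is vaccinated, as in section 9.7. State that a reference who re-enters as a recipient takes the vaccinated role only in the new pair.
- Delete the outcome-date/end-of-period clause.

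The cost is one paragraph of Protocol wording and the matching line in the common script. No new data are needed. The existing caution about few pre-period events should stay, since fixing the label does not add events.

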	Efluelda Tetra®	QIV, adjuvanted (high-dose)	Individuals in long term care facilities (nursery homes for elderly) only

Outcomes

We will estimate VE against the laboratory-confirmed influenza outcomes listed below.

Table 4. Laboratory-confirmed influenza outcomes

Variable	Country	Data source and details
Laboratory-confirmed influenza A	Denmark	Danish Microbiology Database . Defined as a laboratory-confirmed positive influenza test with a known subtype of influenza A.
	Finland	National Infectious Diseases Register . Defined as a laboratory-confirmed positive influenza test with a known subtype of influenza A.

	Sweden	Register on surveillance of notifiable communicable diseases (SmiNet). Defined as a laboratory-confirmed positive influenza test with a known subtype of influenza A.
Laboratory-confirmed influenza B	Denmark	Danish Microbiology Database. Defined as a laboratory-confirmed positive influenza B test result.
	Finland	National Infectious Diseases Register. Defined as a laboratory-confirmed positive influenza B test result.
	Sweden	Register on surveillance of notifiable communicable diseases (SmiNet). Defined as a laboratory-confirmed positive influenza B test result.
Hospitalisation due to influenza	Denmark	The National Patient Register and the Danish Microbiology Database. Defined as a hospitalization with a PCR positive test for influenza within 14 days before to 2 days after the admission date, b) inpatient contact or at least 12 hours of contact, and c) influenza-like illness relevant diagnosis code (ICD-10: J09, J10, J11)
	Finland	National Care Register for Health Care and the National Infectious Diseases Register. Defined as a hospitalization with a PCR positive test for influenza within 14 days before to 2 days after the admission date, b) inpatient contact, and c) influenza-like illness relevant diagnosis code (ICD-10: J09, J10, J11)
	Sweden	The Swedish Patient Register and the Register on surveillance of notifiable communicable diseases (SmiNet). Defined as a hospitalization with a PCR positive test for influenza within 14 days before to 2 days after the admission date, b) inpatient contact or at least 12 hours of contact, and c) influenza-like illness relevant diagnosis code (ICD-10: J09, J10, J11)

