9.4 Data sources

All data sources are nationwide registers in native format. All study investigators have access to their country-specific data and can link data between registers for the purpose of our study. Given the near real-time availability of the data source, our analyses will provide timely evidence. Denmark and Finland will have full data availability for all variables (with no missing data; all the exposures, outcomes, or covariates are either present or not) during the study period and as reporting to national registers is mandatory/structurally implemented, this provides complete follow-up of all residents over time. Currently, Sweden has limited access to nationwide influenza vaccination data but will be able to provide data from four regions in Sweden with a combined population of 1,220,00 individuals. These include Uppsala Region (405,000), Jönköping Region (370,000), Blekinge Region (160,000), and Värmland Region (285,000).

Table 7. Overview of individual-level data sources in the three Nordic countries

Country	Data sources						
Denmark							
Title	Info	Type	Setting	Study availability	Update	Lag	Ref
The Danish Civil Registration System	The register provides the unique personal identifier for all permanent residents of Denmark that allows linkage between all Danish health care registers and civil registrations systems. In addition, it holds general demographic information such as birthdate and sex as well as continuously updated information and dates on historical addresses, immigration and emigration status, and death.	Register	Nationwide	1968- today	Daily	No lag	(24)

The Danish vaccination register	The register holds information on all vaccinations given in Denmark including information on vaccination date, brand, type, dose, and product batch number ever since November 15, 2015 (when reporting to the register became mandatory).	Register	Nationwide	2020 – today	Daily	No lag	(25)
The National patient registry	The register covers all hospital contacts/visits in Denmark with information on the duration of the contact/visit, department of admission and other hospital characteristics. Treating physician-assigned diagnoses have been registered according to ICD-10 codes since 1995.	Register	Nationwide	1995 - today	Daily	No lag	(26)

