The Danish Microbiology Database	Information on positive results of RT-PCR tests for influenza are obtained from The Danish Microbiology Database (MiBa) which holds information on all microbiology samples analysed at Danish departments of microbiology, including information on influenza test results, date of sampling, date of analysis, type of test and interpretation of the test (positive / negative).	Register	Nationwide	2020 – today	Daily	No lag	(27)

Country	Details of the individual-level data sources						
Finland							
Title	Info	Type	Setting	Study availability	Update	Lag	Ref
Finnish Population Information System	The register is held by the Digital and Population Data Services Agency and contains personal data on all permanent residents in Finland such as the unique personal identifier, date of birth, place of residence, date of death, and date of immigration, and emigration.	Register	Nationwide	1964 - today	Daily	No lag	(28)
National Vaccination Register	The register, which is based on the Register of Primary Health Care Visits, holds information on almost all influenza vaccinations administered in Finland; only influenza vaccinations given by social care givers such as nursing homes might be incompletely covered. Data include the date of vaccination, vaccine batch number and trade name.	Register	Nationwide	2009 - today	Daily	No lag	(29)

Care Register for Health Care	The register comprises information on all in-hospital care (since 1969) and outpatient specialist care (since 1998) in Finland, including admission and discharge dates, whether hospitalisation was planned or acute, codes for discharge diagnoses (according to ICD-10) and surgical procedures, whether discharged as deceased, to own private residence or other health care facilities, type of department and hospital. The register is held by the Finnish Institute for Health and Welfare.	Register	Nationwide	1967 - today	Daily	1-4 weeks	(30)
Register for Primary Health Care Visits	The register is held by Finnish Institute for Health and Welfare and holds data on all primary health care services delivered in Finland.	Register	Nationwide	2011 - today	Daily	No lag	(31)

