Swedish national inpatient register	The register comprises information on all in-hospital (since 1987) and out-patient (since 2001) specialist care in Sweden including data on admission and discharge dates, whether hospitalisation was planned or acute, codes for discharge diagnoses and surgical procedures, whether discharged as deceased, to own private residence or other health care facilities, type of department, and hospital. For the current study period discharge diagnoses were recorded according to the Swedish clinical modification of the ICD-10 (i.e. ICD-10-SE). The register is held by the National Board of Health and Welfare.	Register	Nationwide	2017 - today	Monthly	2-4 weeks	(36)
Swedish Prescribed drug register	The Swedish Prescribed Drug Register contains details of all the prescriptions dispensed in Sweden since July 1, 2005. It is updated monthly with around 100 million prescriptions dispensed each year. It covers the entire Swedish population and includes information on unique personal identifier of the patient, age, sex, place of residence, and prescription information on substance, brand name, formulation and package dispensed amount, dosage (in free text) and unique expenditure and reimbursement, date of prescribing and dispensing, practice that has issued the prescription, and prescriber's profession. Drugs are identified by a unique identifier for each specific combination of brand name, substance, formulation, and package. Additionally, all drugs are classified according to the Anatomic Therapeutic Chemical Classification System (ATC). The register only includes filled prescriptions, not medicines sold over the counter, nor medicines administered directly by health-care personnel without prescription. The	Register	Nationwide	2017	monthly	2 weeks	(37)

	register is held by the National Board of Health and Welfare.						
Register on Surveillance of Notifiable Communicable Diseases (Sminet)	The register contains information on notifiable diseases (for which reporting is mandatory) reported by either the analysis-performing laboratories, the treating physician or the autopsy-performing physician, in accordance with the Swedish Communicable Diseases Act. Data include the date of disease occurrence, date of testing, date of positive test and diagnoses. The register is held by the Public Health Agency of Sweden.	Register	Nationwide	2020 - today	Daily	No lag	(38)

Missing data

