$$PERR = \frac{\frac{Event\ Rate_{Vaccinated,current}}{Event\ Rate_{Vaccinated,pre-vaccinated}}}{\frac{Event\ Rate_{Unvaccinated,current}}{Event\ Rate_{Unvaccinated,pre-vaccinated}}}$$

This ratio-of-ratios approach aims to adjust for pre-existing differences between those who choose vaccination and those who do not.

We will use Poisson regression to estimate event rates during the pre-vaccination and current periods. We will report point estimates and 95% confidence intervals for the PERR-adjusted measure of VE (1-PERR). The precision of these estimates will depend on the number of events in the pre-vaccination period. With high vaccine uptake and the vaccination occurring early in the start of the influenza season, the pre-vaccination period may produce fewer events. PERR results will be interpreted carefully and considered alongside the main matched cohort analyses and other supplementary analysis.

Negative control outcomes (NCO)

To evaluate the possible residual confounding in analysis of influenza vaccine effectiveness, we will analyse the association between influenza vaccination and the following negative control outcomes (NCO) in our main study design: Lower back pain (ICD10: M543-M545), clavicle fracture (ICD10: S420), and diverticulitis (ICD: K57).

Analysing negative control outcomes is a way to assess residual confounding. (70) Negative control outcomes such as lower back pain, clavicle fracture, and diverticulitis are conditions biologically unrelated to both vaccination and influenza. Any association between influenza vaccination and these outcomes would suggest residual confounding e.g. by healthcare seeking behaviour which could bias VE estimates. If no associations are found, it supports the validity of the primary analysis. Significant associations would indicate confounding that requires further adjustment or caution in interpretation. This relies on the assumption that the association between influenza vaccination and the negative control outcome is subject to the same confounders as the association between influenza vaccination and the influenza outcomes. Including negative control outcomes strengthens the study's credibility.

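### The negative control outcomes are defined by code alone and K57 is broader than its diverticulitis label, so a null result could falsely reassure about hospitalisation VE

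*Protocol*

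**What the plan says.** The negative control part of Protocol section 9.8 names three outcomes: "Lower back pain (ICD10: M543-M545), clavicle fracture (ICD10: S420), and diverticulitis (ICD: K57". It aligns the population, matching, day-14 start and statistical method with the main cohort analysis. It does not say which contacts count, in which diagnosis position, or whether earlier cases are excluded.

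The section states its working assumption, that "the negative control outcome is subject to the same confounders as the association between influenza vaccination and the influenza outcomes", and gives healthcare seeking as its example of what an association would reveal. It then fixes the reading. No significant association supports the validity of the primary analysis and suggests minimal residual confounding. A significant one signals residual confounding and calls for further exploration or caution.

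Elsewhere the Protocol is more specific. In Table 4 (section 9.3), influenza hospitalisation requires "inpatient contact or at least 12 hours of contact" in Denmark and Sweden, and inpatient contact only in Finland. In Table 5, hospitalisation for acute respiratory infection also requires a primary diagnosis.

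The source registers in Table 7 (section 9.4) are wider than admissions. For Denmark, "The register covers all hospital contacts/visits in Denmark". The Finnish register holds "in-hospital care (since 1969) and outpatient specialist care (since 1998) in Finland", and the Swedish one "all in-hospital (since 1987) and out-patient (since 2001) specialist care in Sweden". The Finnish and Swedish entries also record "whether hospitalisation was planned or acute"; the Danish entry does not mention such a field.

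**The concern.** Two things look wrong.

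First, the label and the code differ. The undivided category K57 is broader than diverticulitis. The same sentence uses four-character codes for the other two controls, so the Protocol can be more precise where it wants to be.

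Second, a code with no contact rule, applied to registers that include outpatient care, picks up whatever those registers hold. Back pain and diverticular disease can persist, so a routine revisit after day 14 could count as an event. Such contacts need not respond to healthcare seeking and frailty in the same proportion as an acute influenza admission does, and the shared-confounder assumption then becomes weak for that outcome.

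At stake is the validity statement attached to VE against influenza hospitalisation. If opposing biases cancel in the control but not in the outcome, the plan's rule turns a null result into unwarranted reassurance.

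**Working it through.** The Protocol states no rate, event count or expected ratio for the negative controls, so there is no figure to reproduce. The check is a comparison of definitions followed by an illustration on assumed values.

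**Definitions side by side**

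| Element | Influenza hospitalisation (Table 4) | Negative controls (section 9.8) |
|---|---|---|
| Contact | Inpatient, or at least 12 hours (Finland: inpatient only) | Not stated |
| Diagnosis position | Not stated | Not stated |
| Further restriction | Positive PCR within a window around admission | None; no exclusion of prior cases |
| Codes | J09, J10, J11 | M543–M545, S420, K57 |

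**Direction of the two confounders.** Table 8 has healthcare seeking raising both vaccination and influenza hospitalisation, so VE is underestimated. High frailty lowers vaccination and raises hospitalisation, so VE is overestimated. Both act on the influenza outcome. What matters is whether a control carries them in similar proportion.

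**Illustration of cancellation.** Let w be the share of control events among the unvaccinated that are planned contacts, RR_planned the vaccinated-to-unvaccinated ratio for planned contacts, and RR_acute the ratio for acute ones. All three are assumptions. RR_acute below 1 represents net frailty-type bias; RR_planned above 1 represents net care-seeking bias.

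RR_mixed = w × RR_planned + (1 − w) × RR_acute

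RR_mixed = 1 when w = (1 − RR_acute) / (RR_planned − RR_acute)

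With RR_acute = 0.8 and RR_planned = 1.2:
- w = 0.25: 0.25 × 1.2 + 0.75 × 0.8 = 0.90
- w = 0.50: 0.50 × 1.2 + 0.50 × 0.8 = 1.00
- w = 0.75: 0.75 × 1.2 + 0.25 × 0.8 = 1.10

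Planned share at which the control looks null:

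| RR_acute | RR_planned 1.1 | RR_planned 1.2 | RR_planned 1.3 |
|---|---|---|---|
| 0.7 | 75% | 60% | 50% |
| 0.8 | 67% | 50% | 40% |
| 0.9 | 50% | 33% | 25% |

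For example, (1 − 0.9) / (1.3 − 0.9) = 0.25 and (1 − 0.7) / (1.1 − 0.7) = 0.75.

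A mixed control can therefore sit at or near 1 while its acute part is biased. The calculation shows that this can happen, not that it will.

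**Which controls are exposed.** Clavicle fracture is an acute injury, so its planned share should be small and the mechanism hardly applies. Back pain and K57 are exposed; their planned shares are not given.

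**The case against.** The strongest objection is that the Protocol is silent on setting rather than wrong about it. A contact rule for a supplementary outcome may stand in an analysis plan that is not shown. Table 5 likewise defines influenza-like illness by code and diagnosis position without a contact rule. This stands as far as it goes: a reader might infer that any hospital contact counts, but the text does not say so. It does not dispose of the K57 mismatch, which is in the stated text, or of the interpretation rule, which is already fixed.

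Healthcare seeking is a confounder that the controls are meant to detect, and Table 8 lists it for influenza hospitalisation. A care-seeking-sensitive control is therefore useful, and laboratory-confirmed influenza has no admission criterion at all. This also stands, and it is why the broad version should be kept.

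Stronger readings are tempting but unsupported:
- **That the check measures planned care.** The planned share is unknown for two controls and should be small for the third.
- **That the plan would infer the wrong direction of bias.** It infers no direction; an association leads only to exploration or caution.
- **That the damage can be sized.** One could assume an acute bias ratio of 0.85 and show a true VE of 40% appearing as 1 − 0.60 × 0.85 = 49%, but this only restates the assumed 0.85.
- **That this check alone settles validity.** It is triangulated with the test-negative design, prior event rate adjustment (introduced for healthy vaccinee bias), regression discontinuity and testing frequency. An unaffected clavicle fracture result could also expose the bias.

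Finally, a restricted control has fewer events. Under a significance rule that makes a reassuring null easier to obtain, so the fix has to address it.

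**Conclusion.** The point holds in a limited form. K57 does not match its label, and the code-only definitions allow the back pain and K57 controls to include outpatient and repeat contacts. A null result could then arise from cancelling biases and be read as minimal residual confounding for hospitalisation VE.

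The size cannot be stated from the documents. The 25% to 75% range for the planned share depends entirely on the assumed ratios. The content of K57 rests on the general ICD-10 classification, because the Protocol prints no code text. The literal any-contact reading assumes that no contact rule is set elsewhere.

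No primary VE estimate changes. What changes is how far the negative controls can be used to vouch for the hospitalisation estimate.

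**What to change.** 1. Reconcile K57 with its label: call it diverticular disease and restrict it to acute admission. The planned/acute field is described for Finland and Sweden only, so state how acute admission is identified in Denmark.
2. For each control, add a version that meets the country's own Table 4 contact criterion (Finland inpatient only; Denmark and Sweden inpatient or at least 12 hours), has the code as primary diagnosis, and excludes people with a same-code contact in the previous 12 months. The comorbidity definitions already use a 7-year look-back in the same hospital registers, so the history should be available.
3. Read hospitalisation VE alongside that version. Keep the any-contact version and present it as a healthcare-seeking indicator.
4. Replace the significance-only reading with one based on the estimate and its confidence interval, so that a wide interval around 1 is not reported as minimal residual confounding.

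The cost is a filter in the common outcome script and one more set of results from the same registers. The downside is fewer events and wider intervals in the restricted version, probably most for back pain; step 4 is there for that reason.
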